4.7.3 Vital signs and physical examination

- (a) Vital signs

At all visits except for Visit 2, blood pressure/pulse rate will be measured in a sitting position.

- (b) Physical examinations

At all visits, general appearance, lymph node, thyroid gland, cardiovascular system, lung, abdomen, musculoskeletal/extremities, and retortion will be examined. Presence/absence of

deterioration or new findings from the baseline (Visit 2) will be checked, and if relevant findings are found, they will be recorded as AEs in the eCRF.

4.8 Volume of blood sampling and handling of biological samples

The total volume of blood that will be drawn from each subject in this study is shown in [Table 6](#).

Table 6 Volume of blood to be drawn from each subject

Assessment		Sample volume (mL)	No. of samples	Total volume (mL)
Hp test		2	1	2
Pepsinogen I/II		2	1	2
Safety	Biochemistry	4	6	24
	Haematology	2	14	28
CYP2C19 genotype		2	1	2
Total				58

If blood samples for Hp test (IgG antibody measurements) and pepsinogen I/II are collected at the same time, a total of 3 mL will be appropriate.

4.8.1 Analysis of biological samples

4.8.1.1 Biochemistry samples

The analyte stability limits defined by _____ will be applied to all analyses performed on behalf of AstraZeneca K.K..

_____ will not analyse samples that fall outside these stability limits. The results will not be reported if found to have been derived from a sample that fell outside these stability limits. The standards of procedure followed by _____ may be amended in accordance with its Standard Operating Procedures.

If _____ chooses to sub-contract the analytical work to another laboratory, _____ must assure itself and provide assurance to AstraZeneca K.K. that the other laboratory will apply defined stability limits to all analyses performed on behalf of AstraZeneca K.K.. Samples falling outside these limits must not be analysed or data reported.

4.9 Genetic tests

4.9.1 Purpose of genetic tests

The purpose of the genetic research is to investigate the genotype of CYP2C19, a metabolising enzyme of D961H known to have two polymorphic genotypes, namely 'extensive metabolisers' (homo- and hetero-types) and 'poor metaboliser'. Since the changes in the blood D961H concentrations show different tendency between the two metabolisers,

they will be examined as a background factor () for criteria for evaluation of phenotypes).

4.9.2 Collection of samples for genetic tests

Subjects will provide a blood sample of 2 mL at screening to be used for genetic test of cytochrome P450 subtype CYP2C19, a metabolising enzyme of D961H.

) will carry out collection of the samples and measurement. The results will be disclosed to AstraZeneca K.K. and the investigator(s).

Genotype is a stable parameter, therefore if for any reason the blood sample is not drawn at screening, it may be taken at any visit until the discontinuation or completion of the study. The blood sample for genotype should be collected at the same time when blood samples for other assessment are collected.

Procedures for sample collection and shipment must be followed as described in

4.9.3 Storage and coding of DNA samples

Special attention is required for conducting a genetic test. The following items should be obeyed to conduct a genetic test and explained to the subjects at the time informed consent is provided:

- Written informed consent to a genetic test must be provided by each subject.
- From the aspect of this study design, implementation of a genetic test is a requirement for the subject to participate in the study.
- From the aspect of this study design, personnel involved in the study at the study centres and AstraZeneca K.K. will have knowledge of genetic information on the subjects based on the genetic test results.
- Samples for the genetic test to be sent to the laboratory will not be labelled with subject identifiers so that the information on the subject will not be revealed to any other parties.
- Samples of the subject who is not enrolled in the study will be destroyed immediately by the study site or
- If the genetic test for the sample of the subject who is not enrolled in the study was completed, the results of the test and the records will be destroyed immediately by

In the case the subject in concern wishes a release of the genetic test results in the informed consent form, the result will be disclosed to the subject via investigator(s) after the database is locked. However, the result will be disclosed to the subject

immediately even before the database is locked only when the subject requests to do so during the study period.

- All samples collected for a genetic test will be used only for CYP2C19 genotyping and will be destroyed immediately by after completion of the genetic test on CYP2C19.

5. DATA MANAGEMENT

Data will be entered in the WBDC system at the study site. Trained study personnel will be responsible for entering data on the observations, tests and assessments specified in the protocol into the WBDC system and according to the eCRF Instructions. The eCRF Instructions will also provide the study site with data entry instructions. Data entered in the WBDC system will be immediately saved to a central database and changes tracked to provide an audit trail. AstraZeneca K.K. will make an inquiry to the investigator(s) for missing, unreal, or conflict data that have been entered using the WBDC system. When data have been entered, reviewed, edited and Source Data Verification performed the principal investigator will be notified to sign the eCRF electronically as per the agreed project process and data will be locked to prevent further editing. A copy of the eCRF will be archived at the study site. Quality control procedures will be applied to each stage of the data handling to ensure that all data are reliable and have been processed correctly.

6. STATISTICAL METHODS AND DETERMINATION OF SAMPLE SIZE

6.1 Statistical evaluation – general aspects

A comprehensive Statistical Analysis Plan (SAP) will be prepared before the database lock.

Only descriptive analysis will be used in this study.

All statistical analyses in this study will be performed by Statistics and Programming Department of AstraZeneca K.K. using the SAS software.

6.2 Description of outcome variables in relation to objectives and hypotheses

6.2.1 Primary variable

The primary variables of this study are as follows:

Safety variables

- AEs
- Clinical laboratory values

- Vital signs

6.2.2 Secondary variables

The secondary variables of this study are as follows:

Efficacy variables

- Presence or absence of gastric and/or duodenal ulcers at Weeks 4, 12, 24 and 52 after initial administration
- Severity of gastric mucosal lesion by modified LANZA score at Weeks 4, 12, 24 and 52 after initial administration
- Presence/absence and severity of NSAID-associated GI symptoms assessed by the investigator(s) every 4 weeks from Week 4 to Week 52 after initial administration

6.3 Description of analysis sets

The safety analysis set for the safety evaluation as the primary objective will include all subjects who take at least one dose of study medication, and who have data after initial administration.

The analysis of the efficacy variables that is the secondary objective will be performed using a full-analysis-set (FAS). For gastric and/or duodenal ulcer free status, the analysis based on a per-protocol-set (PPS) will be also performed.

The FAS will consist of all subjects registered to the study who took at least one dose of study medication and who had no active/current gastric or duodenal ulcer at baseline. The PPS will be a subset of subjects from the FAS, and those who comply restrictions of the study treatment without any serious protocol deviations or violations.

All analysis sets will be determined before database lock.

6.4 Method of statistical analysis

6.4.1 Primary variable

The safety evaluation of D20 as the primary objective of this study will be performed based on AEs, clinical laboratory values and vital signs using the safety analysis set.

- (a) AEs

All AEs will be classified by system organ class and by preferred term using MedDRA and those occurred at baseline and after administration of the investigational products will be summarised in separate lists. AEs occurred after administration of the investigational products will be classified by system organ class and by preferred term using MedDRA. Data on drug-related AEs will be collected in the same manner, as required. The number of subjects who developed AEs, drug-related AEs, SAEs, and AEs led to withdrawal from the

study will be summarised, together with the total number of AEs, drug-related AEs, SAEs and AEs led to withdrawal from the study.

(b) Clinical laboratory values

Quantitative data of clinical laboratory values will be summarised for each measurement using descriptive statistics. Descriptive statistics of the changes from baseline (at screening) will also be summarised. Qualitative data will be summarised for each measurement using frequency table. Values before baseline and values of each measurement will be summarised in cross tables.

(c) Vital signs

Quantitative data of vital signs will be summarised for each measurement using descriptive statistics. Descriptive statistics of the changes from baseline (at screening) will also be summarised.

6.4.2 Secondary variables

Secondary variables, the efficacy variables, will be analysed using the FAS . For presence/absence of gastric and/or duodenal ulcer, the analysis based on PPS will be also performed.

6.4.2.1 Gastric and/or duodenal ulcer free status

The following two methods will be used to calculate each proportion of subjects without gastric and/or duodenal ulcer (ulcer-free rate) in FAS and PPS. The population excluding subjects who are declared not to have an ulcer scar by the central evaluation committee at baseline will be evaluated (see Section 6.7). In this analysis, the evaluation of the central committee for the presence/absence of gastric and/or duodenal ulcer after dosing will be used.

[Ulcer-free rate by the Kaplan-Meier method]

It will be defined as an event if gastric and/or duodenal ulcer is observed by EGD and the plots to show the period from the date of initial administration to the date of event occurred will be constructed using the Kaplan-Meier method. Data obtained from the subjects who have not developed ulcer throughout the study period will be cut off on the day of the last test with EGD. Ulcer free rates of gastric and/or and duodenal ulcer at Week 4, 12, 24 and 52 and its 95% confidence intervals will be calculated by the constructed Kaplan-Meier plots.

[Ulcer-free rate by EGD performed at each measurement]

Subjects who remained gastric and/or duodenal ulcer-free status confirmed by the EGD at Weeks 4, 12, 24 and 52 after the initial administration or those who discontinued the study by reason that gastric and/or duodenal ulcer-free status was confirmed before performing the EGD at each measurement will be considered as ulcer-free subjects and the proportion of the ulcer-free subjects will be calculated against the entire number of the subjects included in the

analysis population, and its 95% confidence intervals will be calculated. The proportion of the ulcer-free subjects will be stratified by the following factors to calculate the percentages for each subgroup.

- Sex (Male, Female)
- Age (<65, 65-74, 75≤)
- Hp positive/negative
- Number of types of NSAID (one or more types)
- Use of steroidal agent(s) (Yes or No)
- Genotypes of CYP2C19 (homo EM, hetero EM, PM)
- Underlying diseases (e.g., osteoarthritis, rheumatoid arthritis, lumbago)
- Degree of gastric mucosa atrophy (positive or negative)
Positive: Concentration of pepsinogen I is 70.0 ng/mL or below and pepsinogen I/II is 3.0 or below
Negative: Concentration of pepsinogen I is 70.1 ng/mL or above or pepsinogen I/II is 3.1 or above
- Extension of gastric mucosa atrophy (no atrophy, C-1, C-2, C-3, O-1, O-2, O-3)

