The study is a multicentre, open-label, single arm, long term study involving patients with a history of gastric and/or duodenal ulcers receiving daily NSAID therapy.

Target subject population

Patients aged 20 years and above with a history of gastric and/or duodenal ulcers (diagnosed having osteoarthritis, rheumatoid arthritis, lumbago, etc.) who are receiving daily NSAID therapy.

Test product, dosage and mode of administration

In this study the following test products will be used:

- D961H 20 mg-capsules

Patients will receive one D961H 20 mg capsule once daily orally after breakfast for 52 weeks.

Comparator, dosage and mode of administration

In this study any comparator will not be used.

Duration of treatment

52 weeks

Outcome variables

- **Safety**
 - **Primary outcome variables:**
 - AEs
 - Clinical laboratory values
 - Vital signs
- **Efficacy**
 - **Secondary outcome variables:**

- Presence or absence of gastric and/or duodenal ulcers at Weeks 4, 12, 24 and 52 after initial administration
- Severity of gastric mucosal lesion by modified LANZA score at Weeks 4, 12, 24 and 52 after initial administration
- Presence/absence and severity of NSAID-associated gastrointestinal (GI) symptoms assessed by investigator(s) every 4 weeks from Week 4 to Week 52 after initial administration

Statistical methods

In this study, no hypothesis will be tested.

For safety variables, quantitative data will be summarised using descriptive statistics and qualitative data will be summarised using a frequency table.

For gastric and/or duodenal ulcer free status, ulcer-free rates of gastric and/or duodenal ulcer at Week 4, 12, 24 and 52 and their 95% confidence intervals will be calculated by Kaplan-Meier Method. Also, ulcer-free rates based on EGD results of each measurement and its 95% confidence intervals will be calculated. Modified LANZA scores will be summarised for each measurement using descriptive statistics, and descriptive statistics of the changes from baseline will also be summarised. Presence/absence and severity of NSAID-associated GI symptoms will be summarised using a frequency table.

Since results from this study will be submitted for application for drug approval, interim analysis will be performed when 24-week data are locked.

TABLE OF CONTENTS	PAGE
TITLE PAGE	1
PROTOCOL SYNOPSIS.....	2
TABLE OF CONTENTS.....	5
LIST OF ABBREVIATIONS AND DEFINITION OF TERMS	9
1. INTRODUCTION	11
1.1 Background.....	11

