3. STUDY PLAN AND PROCEDURES

3.1 Overall study design and flow chart

This Clinical Study Protocol has been subjected to a peer review according to AstraZeneca standard procedures.

This study is designed as a multicentre, open-label, single arm, long-term study involving patients with a history of gastric and/or duodenal ulcers receiving daily NSAID therapy.

A total of 130 patients with a history of gastric and/or duodenal ulcers with ulcer scar confirmed by the esophagogastroduodenoscopy (EGD) performed at screening will receive D20.

The safety of the concomitant use of D961H and NSAID for a long-term period will be assessed. The efficacy of D20 will be also assessed after 52-week oral administration based on the results of the EGD performed at Weeks 4, 12, 24 and 52 after initial administration to verify presence or absence of gastric and/or duodenal ulcers, and to evaluate the severity of gastric and/or duodenal mucosal lesion at Weeks 4, 12, 24 and 52 after initial administration according to modified LANZA score, and investigator's assessment for presence/absence and severity of GI symptoms performed every 4 weeks. If development of gastric and/or duodenal ulcer is observed, the patient will be discontinued from the study.

Findings of EGD including those judged from screening results with an evidence of an ulcer scar and those judged by the investigator(s) after initial administration as gastric and/or duodenal ulcers will be reviewed as needed by the central evaluation committee (see Section 6.7) established by AstraZeneca K.K..

An interim analysis will be performed when 24-week data is locked. The results from this analysis will be submitted to the authority for application for drug approval.

[Table 2](#) shows the study plan including frequency and time of visits.

Table 2 Study Plan

Period	Screening		Study Treatment								
	1	Regis- tration 2	3	4	5	6 7	8	9 10	11	12 13 14	15 or at disc onti nuat ion ^k
Number of weeks before and after Visit 2	2W – 0	0	4W	8W	12W	16W 20W	24W	28W 32W	36W	40W 44W 48W	52W -
Time window	-	-	±4d	±4d	±4d	±4d	±4d	±7d	±7d	±7d	±7d
Informed consent ^a	X										
Inclusion/exclusion criteria	X	X									
Demographic data	X										
Medical/surgical history	X										
Complications	X	X									
Physical examination	X	X	X	X	X	X	X	X	X	X	X
Vital signs	X		X	X	X	X	X	X	X	X	X
Clinical laboratory tests ^{b, c}	X		X	X ^l	X	X ^l	X	X ^l	X	X ^l	X
Pregnancy test (urine) ^d	X										
Hp test (IgG antibody)	X ^m										

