4.6.1 Presence/Absence of gastric and/or duodenal ulcer

4.6.1.1 Methods of assessment

At Visits 1, 3, 5, 8 and 15 (at screening, Weeks 4, 12, 24 and 52 after initial administration), EGD will be performed in the fasting state to confirm presence/absence of gastric and/or

duodenal ulcer based on the following criteria. If gastric and/or duodenal ulcer is present, the site, stage (the Sakita/Miwa classification) and longitudinal diameter of ulcer will be recorded in the eCRF.

Presence/Absence of gastric and/or duodenal ulcer

If gastric and/or duodenal ulcer is verified by EGD and is in the active stage (A1 or A2) or in the healing stage (H1 or H2) according to the Sakita/Miwa classification, “presence of ulcer” should be defined.

Site of ulcers:

Site I: cardia part, fornix, upper gastric corpus, middle gastric corpus, lower gastric corpus, gastric angle, pyloric vestibular part, bulb, retrobulbar region

Site II: anterior wall, posterior wall, greater curvature, lesser curvature

Stage (Sakita/Miwa classification)

Active stage:

A1: Slough in the ulcer is thick with inflammatory swelling in the marginal area.

A2: Circumferential white ring and hyperemia are seen in the marginal area of the ulcer.

Healing stage:

H1: The ulcer is shrunk with redness in the marginal area, and mucosal plicae are gathering.

H2: The ulcer is further healed and upheaved, being covered with thin slough

Scar stage:

S1: so-called ‘Red Scar’: Hyperemia still remains in the centre of the scar.

S2: so-called ‘White Scar’: Hyperemia in the scar disappears, turning into the same colour as adjacent mucosa.

The longitudinal diameter

The longitudinal diameter will be measured referring such as endoscopy forceps. If several ulcers are found, record the longitudinal diameter of the largest ulcer.

EGD images

For the central review of confirmation about presence/absence of gastric and/or duodenal ulcer, EGD images showing the sites judged to be the scar of ulcers at screening and the sites

judged to be the ulcers during the treatment period with the investigational product (one each of close and distant views. The same is required for EGD images in the past used for a lesion with unclear scar) will be submitted to AstraZeneca K.K.. The personal information (such as the name and the medical record number) which can specify the patient should be masked before submission to AstraZeneca K.K..

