6.7 Central evaluation committee

For this study, a central evaluation committee that consists of experts in gastroenterology will be established to confirm the rationale for judgement by the investigator(s) based on the EGD.

The board will review the findings of the baseline EGD that was judged as the scar of ulcer and EGD images taken before screening and used for eligibility assessment due to unclear scar at baseline, and EGD images by which the investigator(s) confirmed gastric and/or duodenal ulcer after initial administration as needed, and report the results of the review to AstraZeneca K.K..

Time to hold the meeting and the responsibilities of the board members will be determined separately.

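### Central review of post-dose ulcers runs in one direction only and is optional, so the committee-based ulcer-free rate can never fall below the investigator-based rate, which the plan does not report

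*Protocol*

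**What the plan says.** Section 6.4.2.1 defines two ulcer-free rates, one by Kaplan-Meier and one by visit, and fixes the reading behind both: "In this analysis, the evaluation of the central committee for the presence/absence of gastric and/or duodenal ulcer after dosing will be used".

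Three other places set what the committee sees after dosing:

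- Section 3.1: findings "those judged by the investigator(s) after initial administration as gastric and/or duodenal ulcers will be reviewed as needed by the central evaluation committee".
- Section 6.7: the board reviews "EGD images by which the investigator(s) confirmed gastric and/or duodenal ulcer after initial administration as needed".
- Section 4.6.1.1 (EGD images): the post-dose images to be submitted are those of sites "judged to be the ulcers during the treatment period with the investigational product", one close and one distant view each.

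The committee also reviews baseline scar images, but these only decide who enters the analysis population. No section sends it a post-dose EGD that the site read as negative.

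On the consequence of a called ulcer, Section 3.1 says: "If development of gastric and/or duodenal ulcer is observed, the patient will be discontinued from the study".

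**The concern.** The reading that decides the endpoint exists only for EGDs that were already positive on site. For all others the analysis must tacitly take over the investigator's negative call. The committee can overrule the investigator in one direction and has no means of doing so in the other.

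The design gives no protection against this. In the protocol's words, "The study is a multicentre, open-label, single arm, long term study". No control arm passes through the same filter, so the absolute rate stands alone. The 24-week results go into the approval application (Sections 3.1 and 6.6). With only the committee-based rate planned, a reader of those results could not see how far review had moved it.

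The qualifier *as needed* adds a second difficulty. No criterion says which called ulcers are reviewed, and Section 6.4.2.1 does not say which reading counts when one is not.

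**Working it through.** The protocol gives no expected ulcer-free rate and no reader agreement, so there is no planned figure to reproduce. The check is one of logic, followed by illustrations on stated assumptions.

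**1. Paths through the review**

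| Investigator's reading | Committee | Status in the analysis |
|---|---|---|
| No ulcer | Never sees the images | Ulcer-free |
| Ulcer | Confirms | Event |
| Ulcer | Overturns | No event |
| Ulcer | Not reviewed | Not defined |

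Let N be the subjects analysed, I the subjects with a called ulcer, and V the calls overturned, with 0 ≤ V ≤ I.

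- Investigator-based rate = 1 − I/N.
- Committee-based rate = 1 − (I − V)/N, which is never lower.

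The inequality holds whether unreviewed calls are taken as events or as non-events.

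For Kaplan-Meier, subjects without an event "will be cut off on the day of the last test with EGD". An overturned event thus becomes a censoring at the same EGD. With d events among n at risk, the factor 1 − d/n becomes 1 − (d − 1)/n, which is larger. Later risk sets do not change, because the subject has left the study in any case. The curve from that time on is equal or higher.

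**2. Size against the investigator's reading**

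Table 1 (Section 1.2) gives 5.2% and 5.3% cumulative incidence at 6 months on D20. At a constant hazard, the one-year figures are 1 − (1 − 0.052)² = 10.1% and 1 − (1 − 0.053)² = 10.3%. About 13 of 130 is therefore assumed for one year, and 7 of 130 for six months. The numbers overturned are also assumed. Intervals are exact (Clopper-Pearson) 95%.

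| Called | Overturned | Ulcer-free | 95% CI |
|---|---|---|---|
| 13 | 0 | 117/130 = 90.0% | 83.5-94.6 |
| 13 | 1 | 118/130 = 90.8% | 84.4-95.1 |
| 13 | 2 | 119/130 = 91.5% | 85.4-95.7 |
| 13 | 3 | 120/130 = 92.3% | 86.3-96.2 |
| 7 | 0 | 123/130 = 94.6% | 89.2-97.8 |
| 7 | 3 | 126/130 = 96.9% | 92.3-99.2 |

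These shifts measure the distance from the investigator's reading. They do not measure bias.

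**3. Size against the truth**

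Let p be the true ulcer rate and Se the share of ulcers that investigators detect. If the committee is always right on what it sees, the expected committee-based rate is 1 − p·Se.

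| p | True rate | Se = 100% | Se = 90% | Se = 80% |
|---|---|---|---|---|
| 5.3% | 94.7% | 94.7% | 95.2% | 95.8% |
| 10% | 90.0% | 90.0% | 91.0% | 92.0% |

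The upward bias is p(1 − Se): 0 to 1.1 points in the first row and 0 to 2 points in the second. It is zero when nothing is missed. Wrongly overturned true ulcers would add to it.

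The net error can also be downward if the committee retains false calls. With p = 5.3%, Se = 100%, 3% of ulcer-free subjects falsely called and half of those calls kept, the rate is 1 − (0.053 + 0.947 × 0.03 × 0.5) = 93.3%, against a true 94.7%.

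**The case against.** The strongest reply is that an overturned call may be a false positive, so that removing it moves the rate towards the truth. That stands. A reader might infer from the one-way flow that the rate is necessarily inflated, or take the step from 90% to about 92% as the size of the bias. The documents support neither. They give no rate of missed ulcers and no rate of wrong overturns, and a correct overturn is the purpose of the review.

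A reader might also infer that a subject withdrawn for an ulcer that is later overturned is credited as ulcer-free to Week 52 in the visit-based rate. The clause on discontinued subjects in Section 6.4.2.1 is too unclear to say so, and in the Kaplan-Meier analysis the subject is simply censored at that EGD.

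The illustration has limits, which also stand. The one-year figure compounds overseas six-month rates from patients with an ulcer history or aged over 60. The denominator of 130 is an upper limit, since subjects whose scar the committee rejects are left out.

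It can be said as well that an investigator-based analysis needs no new data, because ulcer findings are already in the eCRF, and that the SAP may add it. This is so, and the absence of a sensitivity analysis is not in itself the fault. The fault is in what the protocol does fix: a decisive reading that is available for only one side of the investigator's judgement, and then at discretion.

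**Conclusion.** The point holds as a matter of structure. As written, the committee-based ulcer-free rate can only equal or exceed the investigator-based rate, and a called ulcer that is not reviewed has no status in the analysis. Nothing elsewhere in the protocol repairs either gap.

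The extent of any bias against the truth is unknown. It depends on missed ulcers and wrong overturns. On the assumed detection rates of 80-100% with an error-free committee, it is about 0 to 2 points, which is small beside the sampling error at this sample size. It would nonetheless be systematic, and the confidence interval does not reflect it.

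The severity is moderate. A reader might take this as a fault that invalidates the trial's conclusion, but the primary objective is safety, the sample size rests on safety exposure, efficacy against placebo is studied in another trial (Section 1.2), and "Only descriptive analysis will be used in this study". No decision rule depends on the rate.

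**What to change.** 1. In Sections 3.1 and 6.7, delete the qualifier *as needed* for post-dose findings, so that the committee reviews every EGD on which the investigator called an ulcer. Section 4.6.1.1 already requires those images to be submitted.
2. In Section 6.4.2.1, keep the committee-based rate. Add the same Kaplan-Meier and visit-based rates with the event defined by the investigator's EGD reading. Subjects withdrawn for an ulcer that the committee overturned then count as events in the second set.
3. Report the number of called ulcers and the number overturned.
4. State that negative post-dose EGDs were not centrally read, so that neither rate corrects for missed ulcers.

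The cost is slightly more committee work, one extra analysis, and a second rate that is equal or lower. Making the investigator's reading the main analysis is not recommended: it would not recover missed ulcers either, and it would give up independent confirmation in an open-label study. Only central reading of all negative EGDs, or of a sample of them, would address missed ulcers, at a greater cost in images and reader time.
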